## **6.1.1** Dose Levels for Dose Reductions

Table 1 Dose reductions for olaparib\*

Initial Dose	Following re-challenge post interruption: Dose reduction	Dose reduction 2
300mg twice daily	250mg twice daily	200mg twice daily

\*see section 6.1 for more specific guidance

Once dose is reduced, escalation is not permitted except as indicated in section 5.2.2. for temporary dose reductions association with concomitant use of CYP3A inhibitors or inducers.

# 6.2 Management of Hematological Toxicity

# **6.2.1** Management of Anemia

Table 2 Management of anemia

Hemoglobin	Action to be taken
$Hb < 10 \ but \ge 8 \ g/dl$	Give appropriate supportive treatment and investigate causality.
(CTCAE Grade 2)	Site investigator judgement to continue olaparib with supportive treatment
	(e.g. transfusion) or interrupt dose for a maximum of 4 weeks.
	If repeat Hb $< 10 \ but \ge 8 \ g/dl$ , dose interrupt (for max of 4 weeks) until
	Hb $\geq$ 10 g/dl and upon recovery dose reduction to 250 mg twice daily as a
	first step and to 200 mg twice daily as a second step may be considered.
Hb < 8 g/dl (CTCAE Grade 3)	Give appropriate supportive treatment (e.g. transfusion) and investigate causality. Interrupt olaparib for a maximum of 4 weeks. until improved to Hb $\geq$ 10 g/dl. Upon recovery dose reduce to 250 mg twice daily as a first step and to 200 mg twice daily as a second step in the case of repeat Hb decrease.

Common treatable causes of anemia (e.g., iron, vitamin B12 or folate deficiencies and hypothyroidism) should be investigated and appropriately managed. In some cases, management of anemia may require blood transfusions. For cases where subjects develop prolonged hematological toxicity ( $\geq 2$  week interruption/delay in study treatment due to CTC Grade 3 or worse anemia and/or development of blood transfusion dependence), refer to Section 6.2.3 for the management of this.

Version Date: 15MAY2019 Confidential Page 33 of 60

# 6.2.2 Management of Neutropenia, Leukopenia and Thrombocytopenia

Table 3 Management of neutropenia, leukopenia and thrombocytopenia

Toxicity	Study treatment dose adjustment
CTCAE Grade 1-2	Investigator judgement to continue treatment or if dose interruption, this should be for a maximum of 4 weeks; appropriate supportive treatment and causality investigation
CTCAE Grade 3-4	Dose interruption until recovered to CTCAE gr 1 or better for a maximum of 4 weeks. If repeat CTCAE grade 3-4 occurrence, dose reduce olaparib to 250 mg twice daily as a first step and 200 mg twice daily as a second step

Adverse event of neutropenia and leukopenia should be managed as deemed appropriate by the investigator with close follow up and interruption of study drug if CTC Grade 3 or worse neutropenia occurs.

Primary prophylaxis with Granulocyte colony-stimulating factor (G-CSF) is not recommended, however, if a patient develops febrile neutropenia, study treatment should be stopped and appropriate management including G-CSF should be given according to local hospital guidelines. Please note that G-CSF should not be used within at least 24 hours (7 days for pegylated G-CSF) of the last dose of study treatment unless absolutely necessary. Platelet transfusions, if indicated, should be done according to local hospital guidelines.

For cases where subjects develop prolonged hematological toxicity ( $\geq 2$  week interruption/delay in study treatment due to CTC grade 3 or worse), refer to Section 6.2.3.

# **6.2.3 Management of Prolonged Hematological Toxicities While on Study Treatment** If a patient develops prolonged hematological toxicity such as:

- ≥ 2 week interruption/delay in study treatment due to CTC Grade 3 or worse anaemia and/or development of blood transfusion dependence
- $\geq$  2 week interruption/delay in study treatment due to CTC Grade 3 or worse neutropenia (ANC < 1 x  $10^9$ /L)
- $\geq$  2 week interruption/delay in study treatment due to CTC Grade 3 or worse thrombocytopenia and/or development of platelet transfusion dependence (Platelets < 50 x  $10^9$ /L)

Check weekly differential blood counts including reticulocytes and peripheral blood smear. If any blood parameters remain clinically abnormal after 4 weeks of dose interruption, the patient should be referred to hematologist for further investigations. Bone marrow analysis and/or blood cytogenetic analysis should be considered at this stage according to standard hematological practice. Study treatment should be discontinued if blood counts do not recover to CTC Grade 1 or better within 4 weeks of dose interruption.

Development of a confirmed myelodysplastic syndrome or other clonal blood disorder should be reported as an SAE and full reports must be provided by the site investigator to HCRN who will then report to AstraZeneca Patient Safety (See Section 11). Olaparib treatment should be discontinued if patient's diagnosis of MDS and/or AML is confirmed.

Version Date: 15MAY2019 Confidential Page 34 of 60

# 6.3 Management of Non-Hematological Toxicity

Repeat dose interruptions are allowed as required, for a maximum of 4 weeks on each occasion. If the interruption is any longer than this the sponsor-investigator must be informed. Where toxicity reoccurs following re-challenge with study treatment, and where further dose interruptions are considered inadequate for management of toxicity, then the patient should be considered for dose reduction or must permanently discontinue study treatment.

Study treatment can be dose reduced to 250 mg bid as a first step and to 200 mg bid as a second step. Treatment must be interrupted if any NCI-CTCAE Grade 3 or 4 adverse event occurs which the site investigator considers to be related to administration of study treatment.

# 6.3.1 Management of New or Worsening Pulmonary Symptoms

If new or worsening pulmonary symptoms (e.g., dyspnea) or radiological abnormalities occur in the absence of a clear diagnosis, an interruption in study treatment dosing is recommended and further diagnostic workup (including a high resolution CT scan) should be performed to exclude pneumonitis.

Following investigation, if no evidence of abnormality is observed on CT imaging and symptoms resolve, then study treatment can be restarted, if deemed appropriate by the site investigator. If significant pulmonary abnormalities are identified, these need to be discussed with the sponsor-investigator. If pneumonitis is confirmed, discontinue olaparib.

# 6.3.2 Management of Nausea and Vomiting

Events of nausea and vomiting are known to be associated with olaparib treatment. In study D0810C00019 nausea was reported in 71% of the olaparib treated subjects and 36% in the placebo treated subjects and vomiting was reported in 34% of the olaparib treated subjects and 14% in the placebo treated patients. These events are generally mild to moderate (CTCAE grade 1 or 2) severity, intermittent and manageable on continued treatment. The first onset generally occurs in the first month of treatment for nausea and within the first 6 months of treatment for vomiting. For nausea, the incidence generally plateaus at around 9 months, and for vomiting at around 6 to 7 months.

No routine prophylactic anti-emetic treatment is required at the start of study treatment; however, subjects should receive appropriate anti-emetic treatment at the first onset of nausea or vomiting and as required thereafter, in accordance with local treatment practice guidelines. Alternatively, olaparib tablets can be taken with a light meal/snack (i.e. 2 pieces of toast).

As per international guidance on anti-emetic use in cancer subjects (ESMO, NCCN), generally a single agent antiemetic should be considered eg dopamine receptor antagonist, antihistamines or dexamethasone.

# 6.3.3 Renal Impairment

If subsequent to study entry and while still on study therapy, a patient's estimated CrCl falls below the threshold for study inclusion, retesting should be performed promptly.

Version Date: 15MAY2019 Confidential Page 35 of 60

A dose reduction is recommended for subjects who develop a decline in renal function as defined by a calculated creatinine clearance by Cockcroft-Gault equation of between 31 and 39 ml/min for any reason during the course of the study: the dose of olaparib should be reduced to 200mg BID.

Olaparib should be discontinued if the calculated creatinine clearance declines to  $\leq 30$  ml/min.

# 6.4 Interruptions for Intercurrent Non-Toxicity Related Events

Study treatment dose interruption for conditions other than toxicity resolution should be kept as short as possible. If a patient cannot restart study treatment within 4 weeks for resolution of intercurrent conditions not related to disease progression or toxicity, the case should be discussed with sponsor-investigator.

All dose reductions and interruptions (including any missed doses), and the reasons for the reductions/interruptions are to be recorded in the eCRF.

Study treatment should be stopped at least 3 days prior to planned surgery. After surgery study treatment can be restarted when the wound has healed. No stoppage of study treatment is required for any needle biopsy procedure.

Study treatment should be discontinued for a minimum of 3 days before a patient undergoes radiation treatment. Study treatment should be restarted within 4 weeks as long as any bone marrow toxicity has recovered.

# 6.5 Protocol Therapy Discontinuation

In addition to discontinuation from therapy related to toxicities as outlined above, a subject will also be discontinued from protocol therapy and followed per protocol under the following circumstances outlined below. The reason for discontinuation of protocol therapy will be documented on the electronic case report form (eCRF)

- Documented disease progression
- Site investigator determines a change of therapy would be in the best interest of the subject
- Subject requests to discontinue protocol therapy, whether due to unacceptable toxicity or for other reasons
  - o In a subject decides to prematurely discontinue protocol therapy ("refuses treatment"), the subject should be asked if he or she may still be contacted for further scheduled study assessments. The outcome of that discussion should be documented in both the medical records and in the eCRF.
- Female subject becomes pregnant
- Bone marrow findings consistent with myelodysplastic syndrome (MDS)/acute myeloid leukemia (AML)
- Pneumonitis
- Protocol therapy is interrupted for > 4 weeks.

Version Date: 15MAY2019 Confidential Page 36 of 60

# **6.6** Protocol Discontinuation

If a subject decides to discontinue from the protocol (and not just from protocol therapy) all efforts should be made to complete and report study assessments as thoroughly as possible. A complete final evaluation at the time of the subject's protocol withdrawal should be made with an explanation of why the subject is withdrawing from the protocol. If the reason for removal of a subject from the study is an adverse event, it will be recorded on the eCRF.

Version Date: 15MAY2019 Confidential Page 37 of 60

# 7. STUDY CALENDAR & EVALUATIONS

Study Evaluation Cycle = 28 days	Screening	Treatment	Tumor	Safety Follow Up Visit 	Survival Follow Up 
	-28 days	Cycle 1 + Day 1 ± 2 days	Assessments  ± 7 days	30 Days Post Treatment (±7 days)	Every 3 Months (±7 days)
REQUIRED ASSESSMENTS					
Informed Consent	X				
Medical History 	X				
Physical Exam	X	X		X	
Vital signs and ECOG Performance Status 	X	X		X	
Documentation of DDR alteration in CLIA lab assay 	X				
ECG 	$X^4$				
AEs & Concomitant Medications	X	X		X	
LABORATORY ASSESSMENTS					
Complete Blood Cell Count with diff (CBC) 	X	X		X	
Comprehensive Metabolic Profile (CMP) 	X	X		X	
PT/INR and aPTT 	X				
Pregnancy test (serum or urine) (WOCBP) 	X	$X^7$			
Urinalysis	X				
DISEASE ASSESSMENT					
CT of chest 	X		$X^8$		
CT or MRI of abdomen and pelvis 	X		$X^8$		
Bone Scan 	X		X8		
TREATMENT EXPOSURE					
Olaparib		X			
CORRELATIVE SAMPLES					
Archival Tumor Tissue 	X				
Collection of tumor tissue obtained as standard of care 				$X^{10}$	
Blood Samples for correlative research 		$X^{11}$		$X^{11}$	
BANKING SAMPLES					
Whole Blood 		$X^{12}$		$X^{12}$	
FOLLOW-UP					
Survival Status, Subsequent Therapy					X

# **Key to Footnotes**

- 1: Medical History should include the following information: (1) Diagnosis and staging to include Tumor Node Metastasis (TNM) staging (2) smoking history, (3) trial awareness question (4) prior cancer treatment history and (5) genetic sequencing information.
- 2: Vital signs to include blood pressure, weight, and height (screening only) and ECOG performance status.
- 3: The laboratory report indicating the presence of a DDR alteration (see eligibility) from a CLIA laboratory is required for registration.
- 4: ECG is required within 7 days prior to starting study treatment.
- 5: If screening (baseline) CBC and CMP were performed within 7 days of Day 1 of treatment, these do not need to be repeated. CMP to include sodium, potassium, chloride, creatinine, blood urea nitrogen; liver function tests (LFTs) to include AST, ALT, total bilirubin, alkaline phosphatase
- 6: Subjects taking warfarin may participate in this study; however, it is recommended that prothrombin time (INR and APTT) be monitored carefully at least once per week for the first month, then monthly if the INR is stable.
- 7: For women of childbearing potential (WOCBP): urine or serum βhCG will be checked at screening and prior to study drug on Cycle 1 Day 1 (only if clinically appropriate). If a urine test is done and it is positive or cannot be confirmed as negative, a serum pregnancy test will be required.
- 8: Tumor imaging to continue near the end of every 2nd cycle (~every 8 weeks) for the first 12 months following Cycle 1 Day 1. After 12 months, tumor assessments will be performed near the end of every 3rd cycle (~every 12 weeks). Imaging selected for each subject should remain the same throughout the study. Bone scan will be obtained at screening if there is any clinical or laboratory suspicion of metastatic bone involvement. If bone scan is positive at baseline for metastases, it will be included with tumor response assessments as noted above.
- 9: All subjects must have adequate archival tissue available; identified at screening and shipped by C1D1 (i.e., at least 15 unstained slides or paraffin block). Archival tissue should represent invasive or metastatic urothelial cancer with a preference for metastatic tissue if available. If acceptable archival tissue is not available, this should be discussed with the sponsor-investigator. Subjects will be consented to optional banking of any remaining tumor samples after protocol-specified studies are complete. Banked samples will be reserved for future unspecified cancer-related research. See Correlative Laboratory Manual (CLM) for additional details.

Version Date: 15MAY2019 Confidential Page 39 of 60

- 10: If a subject has a biopsy at progression or for other clinical reasons as per standard of care, they will be asked permission to store some of this tissue for research directed at mechanisms of resistance. Subjects will also be consented to optional banking of any remaining tumor samples after protocol-specified studies are complete. Banked samples will be reserved for future unspecified cancer-related research. See Correlative Laboratory Manual (CLM) for additional details.
- 11: Serial blood samples will be collected to support biomarker research; There are 4 time points for blood samples to be obtained: (1) pre-dose C1D1, (2) pre-dose C3D1, (3) pre-dose C5D1 and at (4) Progression. If a subject comes off study due to progression, samples may be obtained at the Safety Follow Up visit. See CLM for additional details.
- 12: Serial blood samples will be collected for banking; See CLM for additional details. There are 4 time points for blood samples to be obtained: (1) pre-dose C1D1, (2) pre-dose C3D1, (3) pre-dose C5D1 and at (4) Progression. If a subject comes off study due to progression, samples may be obtained at the Safety Follow Up visit.
- 13: Safety Follow-Up Visit should only occur when subjects permanently stop study treatment for whatever reasons (toxicity, progression, or at discretion of site investigator) and should be performed 30 days (±7 days) after the last dose of treatment. Subjects who have an ongoing Grade ≥ 2 or serious AE (SAE) at this visit will continue to be followed until the AE resolves to Grade ≤ 1 or baseline, deemed clinically insignificant, and/or until a new anti-cancer treatment starts, whichever is earlier.
- 14: Survival Follow Up will occur in all subjects until documented disease progression. Subjects who discontinue treatment for any reason without documented disease progression will be followed for disease progression every 3 months for 2 years from safety follow up visit. Once disease progression is documented, subjects will enter a survival follow up period every 3 months for 2 years from the time of documented progression. Follow up may be accomplished via clinic visit, phone call, or other avenues as appropriate. During this follow up, any radiology imaging results performed should be entered into the EDC system.

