# 2.2.2 Secondary Endpoints

- Adverse events are defined by the NCI Common Terminology Criteria for Adverse Events (NCI CTCAE) v4
- Progression-free survival is defined as the time from Day 1 of treatment until the criteria for disease progression is met as defined by RECIST 1.1 or death as a result of any cause.
- Overall survival is defined as the time from Day 1 of treatment until death as a result of any cause

Version Date: 15MAY2019 Confidential Page 24 of 60

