#### 9.8.9 Overall Survival

Overall survival is defined by the date of enrollment to date of death from any cause.

Version Date: 15MAY2019 Confidential Page 45 of 60

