# 12.2.2 Definition of Secondary Endpoints

- Safety of olaparib, defined as rates of Grade 1-5 toxicity according to CTCAE v4.03.
- PFS, which is defined as the time from initiation of treatment to death or progression, depending on which occurs first (as defined by RECIST 1.1).
- Overall survival (OS), which is defined as the time from initiation of treatment to death.

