# 12.4.2 Analysis Plans for Secondary Objectives

Any subject who receives at least one dose of treatment on this protocol is evaluable for toxicity, progression free survival and overall survival. Toxicity rates will be summarized using frequency tables. Progression free survival and overall survival curves will be based on the Kaplan-Meier method.

Version Date: 15MAY2019 Confidential Page 53 of 60

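### Survival follow-up ends at a time set by each subject's own progression, so overall-survival censoring after about month 26 is not independent of prognosis; the effect is small and its direction is unknown

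*Combined protocol and SAP*

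**What the plan says.** Footnote 14 to the study calendar (section 7) sets a different end of follow-up for three groups.

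- Not yet progressed: "Survival Follow Up will occur in all subjects until documented disease progression". A subject who stays on treatment without progression has no stated limit.
- Progressed: "Once disease progression is documented, subjects will enter a survival follow up period every 3 months for 2 years from the time of documented progression".
- Off treatment without progression: these subjects "will be followed for disease progression every 3 months for 2 years from safety follow up visit". Footnote 13 says that the safety visit "should be performed 30 days (±7 days) after the last dose of treatment", so this limit falls about 25 months after the last dose.

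Section 12.4.2 gives the analysis: "Progression free survival and overall survival curves will be based on the Kaplan-Meier method". Section 12.2.2 defines the endpoint: "Overall survival (OS), which is defined as the time from initiation of treatment to death". Section 2.2.2 agrees ("Overall survival is defined as the time from Day 1 of treatment until death as a result of any cause"), but section 9.8.9 starts the clock elsewhere ("Overall survival is defined by the date of enrollment to date of death from any cause"). None of these says when a living subject is censored for OS, although section 9.8.8 does so for progression-free survival (PFS). No OS landmark, truncation time or sensitivity analysis is planned. The synopsis estimates 36 months of enrollment and 48 months of study duration.

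**The concern.** Kaplan-Meier treats a subject censored alive as having the same future risk of death as those still under observation at that time. Here the time of censoring is set by progression, which is itself a strong predictor of death. An early progressor who is still alive leaves first, and a subject progression-free on drug remains. Once the first of these limits is reached, the risk set is no longer a fair sample of the survivors. What is at stake is the OS tail, and any long-term survival rate read from it.

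**Working it through.** **The plan's own figure.** No figure is stated for OS. The only sample-size figure is for response rate (section 12.3): 27 subjects, 10% versus 28%, one-sided exact test. Rejecting at 6 or more responses of 27 gives a significance level of 0.0471 and power of 0.809, as stated. I use n = 27 below.

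**When the rule starts to act.** A living subject who progresses at month P leaves OS follow-up at P + 24. Because P is above zero, this limit removes nobody by month 24. First scheduled imaging is at about 8 weeks (P of about 2), so the earliest scheduled exit is about 2 + 24 = month 26. For a subject who stops treatment almost at once without progression, the limit is about 1 + 24 = month 25.

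**Who can get that far.** With uniform accrual over 36 months and closure at month 48, the share of subjects whose entry date allows 26 months of follow-up is (48 - 26)/36 = 61%, or about 16 of 27.

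**Size and direction.** The documents give no PFS or OS rates for this population, so the rates below are assumptions spanning a range. The method was an illness-death simulation with 400,000 subjects per scenario, progression seen on an 8-week grid, and OS censored at P + 24. PPS is post-progression survival. The long-PFS subgroup has median 36 months and the long-PPS subgroup median 60 months.

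| Assumed medians (months) | OS at 24, true and KM | OS at 36, true | OS at 36, KM | Difference (points) | Of 27: censored by the rule before month-48 closure | Of 27: at risk at month 30 |
|---|---|---|---|---|---|---|
| PFS 4, PPS 8 | 21.2% | 7.8% | 8.0% | +0.2 | 1.4 | 1.1 |
| PFS 4, PPS 12 | 33.3% | 16.9% | 17.0% | +0.1 | 2.8 | 1.7 |
| 20% long PFS, PPS 8 | 29.4% | 17.4% | 19.5% | +2.1 | 1.2 | 2.4 |
| 20% long PFS, PPS 12 | 39.9% | 25.3% | 28.2% | +2.9 | 2.5 | 2.8 |
| PFS 4, 20% long PPS, rest PPS 7 | 28.9% | 17.3% | 15.9% | -1.4 | 2.6 | 1.5 |
| 20% long PFS and 20% long PPS | 36.4% | 26.0% | 26.8% | +0.8 | 2.3 | 2.7 |

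The pattern has a simple explanation:

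- With homogeneous PFS and a constant hazard after progression, nearly everyone alive at month 30 has progressed. Those removed have the same risk as those kept, so the bias is near zero.
- With a durable progression-free subgroup, the rule keeps low-risk subjects and removes higher-risk ones, and the tail rises.
- If those alive 2 years after progression are selected long survivors, the rule removes low-risk subjects, and the tail falls.

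**The off-treatment limit.** The table omits it. Assuming that 25% stop early for other reasons, a run of the third scenario gave a month-36 estimate of 19.2% instead of 19.6% (true 17.5%), a slight trimming of the upward bias.

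**At the trial's size.** In four of these scenarios I simulated 4,000 trials of 27 with 12 to 48 months of administrative follow-up. The month-36 estimate had a sampling standard deviation of 7.4 to 11.0 points. The rule shifted it by +0.3 to +3.2 points on average. This exceeds the large-sample figure in some rows (+1.5 against +0.2 in the first) and is partly a small-sample effect: when the last subjects at risk are censored, the curve is carried forward flat. It is not clean evidence of direction. In 23% to 47% of trials the curve to month 48 was identical with and without the rule.

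**Median.** Median OS was 13.0 to 18.4 months in every scenario, below 24 and so untouched.

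**The case against.** The strongest case against raising this is that it barely matters here. OS is a descriptive secondary endpoint with no test and no planned long-term rate. Few subjects are affected, the error is well inside sampling error, and a reader who sees one or two subjects at risk would discount the tail anyway. All of that stands on size. It does not remove the point. A confidence interval shows sampling error but not this bias, the plan does not call for numbers at risk, and the remedy costs almost nothing.

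Two stronger readings are tempting, and the documents support neither.

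- A reader might infer that progression-free subjects all stay in while progressors drop out, so that long-term OS will look too good. Footnote 14 also limits those off treatment without progression; only subjects still on drug have no stated limit. The upward direction needs an assumed durable progression-free subgroup. Section 1.6.3 makes a mixture plausible, since some alterations may not confer sensitivity, but gives no rates, and the sign reverses with long post-progression survivors.
- A reader might infer a large late error. With 75% of subjects at median PFS 3 months, 25% at 18 months and median PPS 8 months, a very large sample gives 10.8% against a true 7.9% at month 47, about one third too high. With 27 subjects and 12 to 48 months of follow-up, the same assumptions leave on average 0.8 subjects at risk at month 36 and 0.04 at month 47, and nobody at risk at month 47 in 96% of trials. That is not an estimate this trial could report.

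**Conclusion.** The point holds as a minor one. Following the plan as written makes OS censoring after about month 26 depend on progression, which breaks the independent-censoring assumption of the planned curve, and nothing in the plan addresses it. The large-sample error at month 36 is about -1.5 to +3 points under the assumed rates, and its direction cannot be derived from the documents. About 1 to 3 of 27 subjects are affected if the study closes at the estimated 48 months; if follow-up ran until every footnote-14 window had closed, the same scenarios give 2.8 to 5.8. The response-rate analysis and sample size are not touched.

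**What to change.** Change footnote 14 so that survival status is collected every 3 months for all subjects, whatever their progression or treatment status, until death, withdrawal of consent or one common study cutoff date. Add to section 12.4.2 that OS is censored at the last date known alive, up to that cutoff. Censoring of subjects still in follow-up is then administrative. In simulated trials of this size, a common cutoff changed the month-36 estimate by more than 1 point in about 50% to 70% of trials and slightly reduced its sampling standard deviation. The cost is a few extra contacts, which footnote 14 already allows by phone.

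If footnote 14 is left as it is, report OS rates only to 24 months and show numbers at risk. That window is free of this rule but not of study closure: with uniform accrual, 12/36 = one third of subjects would enter with less than 24 months left. The cost is an unreported sparse tail.

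While editing, give OS one start date, since section 9.8.9 differs from sections 2.2.2 and 12.2.2.
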